4.6.3 Immediately Pre-Treatment

A final eligibility assessment will be conducted immediately pre-treatment to confirm continued eligibility. If the subject meets all eligibility criteria the subject may undergo the NEUROMARK™ procedure on the same day that the screening assessments are performed. Once the subject completes the screening procedures and meets all eligibility criteria, the NEUROMARK™ procedure should be scheduled within 14 days unless otherwise approved by Sponsor. The following evaluations will be performed immediately prior to the study procedure. See Testing and Evaluation Guidelines (**Appendix F**) for evaluation details.

- Confirmation of no indication of COVID-19 infection at the time of treatment.
- Review of concomitant medications.
- Physical exam (height, weight, blood pressure, respiratory rate, heart rate and temperature).
- Endoscopic assessment (recorded).

Once eligibility is confirmed, Subject will be prepared for the treatment following Standard of Care (SOC) for similar procedures and per the manufacturer's IFU (**Appendix B**).

5 ENROLLMENT

Subjects will be considered enrolled once the informed consent is obtained, they meet the study eligibility criteria, and receive treatment.

If for some reason a Subject has consented, but becomes ineligible prior to enrollment, the reason for ineligibility will be documented on the Screening Log and the Subject consent document will be maintained in the site's study records.

Definition of Enrollment: Subjects will be considered enrolled once they are consented, meet eligibility criteria, and have received treatment.

At the time of enrollment, the Subject Sequence Number will be assigned to the Subject.

5.1 Unique Study ID Assignment

At the time of enrollment, a unique study ID will be assigned to the Subject and the unique ID entered on the Screening Log and the Subject Name Log. The site will maintain a Subject name log which will link the unique Subject ID code to the Subject. This log will remain confidential and will not be provided to the Sponsor, but only used for reference when monitoring at the study site.

IMPORTANT: Once a Subject has been assigned a unique study ID code, even if an error is made at the time of assignment, the code should not be changed or fixed. The originally assigned code must remain with the Subject for the entire study.

****ASSIGNMENT OF THE UNIQUE STUDY IDENTIFICATION CODE****

The **unique Subject identification (ID) code** will be made up of

Site # + Subject Sequence Number + Name Code

___ + 3 + _____

Site #: The Sponsor, at the beginning of the study, will assign each site a number that will be used to identify the site throughout the course of the study. The site number will become part of the Subject's unique study identification code.

Example = Site 01

Subject Sequence #: These numbers should be assigned in sequential order. Each site will begin with 301 and assign sequentially within their study center.

Example = Site 01's third (3rd) → Subject Sequence # is: 01- 303

Patient Name Code Assignment: The last two letters of the patient's first name and the last 3 letters of the patient's last name. Example: John Smith = HNITH

Should characters not be available (e.g., Subject's last name is only 2 characters in length), an 'X' may be used in lieu of an alpha character. Example: John Do = HNDOX

Example = Site 01 enrolls their 3rd Subject whose name is John Smith

Unique Subject ID Code Example: 01-303-HNITH

6 INVESTIGATIONAL PROCEDURE

The NEUROMARK™ System device is intended for use by appropriately trained personnel. All investigators and support staff will be provided comprehensive training by Neurent Medical (or its designee) in the handling and use of the device. Treatment will be performed in a clinic or doctor's office by a trained medical professional.

6.1 Procedure

The NEUROMARK™ procedure will be performed following the system's Instructions for Use (IFU) found in **Appendix B**.

Immediately prior to system introduction the Subject will have a local anesthetic administered to the target site per the clinic's standard practice. The local anesthetic used and related procedure will be documented in the Subject's file. Once the Subject is appropriately anesthetized, the NEUROMARK™ procedure may start. Both nasal cavities will be treated during a single treatment session.

Once both nasal cavities have been treated the system will be removed and the procedure will be considered complete.

The procedure may be photographed or videotaped. The Subject's identity will be concealed and patient confidentiality will be maintained.

6.2 Post-Treatment

Following the procedure, an endoscopic assessment of the treatment area will be performed.

Immediately prior to discharge the following will be performed:

- Evaluation of procedure and anesthesia tolerability.
- Assessment for any adverse events or issues.

Reminder: Device Accountability

Each investigational device must be documented on the study's Device Accountability Log.

6.3 Medications and Subject Care

Study Investigator may prescribe pain and/or other post treatment medication as needed. Subjects may take over-the-counter pain medication per Investigator's judgement. Prescription strength pain medication should not be necessary. Should pain medication be prescribed, it will be documented in the Subject's file and any potential related risk will be discussed with the Subject.

Subjects will be asked to refrain from starting a new allergy medication or changing their existing allergy medication regimen, unless instructed otherwise by the study doctor. All medication will be documented in the Subject's chart and medications related to the Subject's sino-nasal condition and/or post procedure discomfort or pain will be evaluated and reported.

6.4 Follow-up evaluations

Subjects will undergo a brief evaluation at 24-48 hours following treatment. This follow-up evaluation may be performed over the phone or in-person.

The following procedures will be performed:

- Evaluation of procedure and anesthesia tolerability.
- Assessment for any adverse events.

- Review and collection of concomitant medications. Any changes to their medications will be documented.

Subjects will undergo additional follow-up evaluation at 1-month, 3-months, 6-months, 9-months and 1-year post treatment. It is preferred that subjects are seen in person; however, due to COVID-19 considerations, portions of the follow up that can be done remotely, may be performed using an online or by phone mechanism to obtain the necessary study data and information concerning the Subject's safety and well-being.

An overview of the evaluations in a checklist format is provided in **Table 1** above.

6.5 Study Exit or Premature Withdrawal

Subjects will be formally exited from the study through completion of the Study Exit CRF at the time of study completion, provided the Subject has not experienced an AE directly attributable to the study device or procedure *that is ongoing and unstable and/or unexplained*.

Subjects may be prematurely terminated or withdrawn from the study for the following reasons:

- Not eligible for treatment.
- Subject starts a medication or treatment that, in the opinion of the Investigator, may skew study results.
- Loss to follow-up (following 3 documented attempts to reach Subject).
- In the physician's opinion, it is not in the best interest of the Subject to continue study participation.
- Subject withdrawal, meaning that Subject voluntarily chooses not to participate in the study.

All subjects enrolled (including those prematurely withdrawn) shall be accounted for and documented.

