11 STATISTICAL ANALYSIS

This is a prospective, single-arm, multicenter, safety and efficacy study.

Summary statistics will be calculated for endpoints and additional evaluations. Categorical variables will be summarized using frequency distributions and continuous variables will be summarized with means and standard deviations (normal distributions) or medians and ranges (non-normal distributions). Confidence intervals (95% CI) may be computed for select study measures.

Each subject serves as their own comparison of pre-procedure to post-procedure outcome scores. Primary efficacy will be assessed based on a reduction in the VAS Nasal Symptom Score as related specifically to rhinitis (rhinorrhea and nasal congestion) from pre-procedure [baseline] to 3 months post-procedure. The statistical methodology is targeted to employ the paired *t*-test and/or its nonparametric equivalent (the Wilcoxon Signed Rank test) with a 2-sided alpha level of 0.05. Additional Evaluations, as listed in the Protocol Synopsis, will be evaluated in a similar manner.

All subjects treated will be included in the safety analyses. All subjects treated who have at least one follow-up will be included in the efficacy analyses. All subjects treated will be included in the safety analyses.

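### Section 6.5 lets treated subjects be withdrawn for starting a medication, and no rule covers their missing scores, so improvement and responder rate may be overstated

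*Combined protocol and SAP*

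**What the plan says.** Section 6.5 introduces its list with "Subjects may be prematurely terminated or withdrawn from the study for the following reasons". One reason is "Subject starts a medication or treatment that, in the opinion of the Investigator, may skew study results". It names no medications, sets no time window and asks for no independent review. The section closes with "All subjects enrolled (including those prematurely withdrawn) shall be accounted for and documented", which is a record-keeping rule and not an analysis rule.

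On medication during follow-up, Section 6.3 says "Subjects will be asked to refrain from starting a new allergy medication or changing their existing allergy medication regimen", but adds "unless instructed otherwise by the study doctor". It also says that "medications related to the Subject's sino-nasal condition and/or post procedure discomfort or pain will be evaluated and reported", without tying this to the efficacy analysis.

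Section 11 describes a within-subject comparison of the VAS NSS for rhinorrhea and congestion, baseline against 3 months, by paired t-test and/or Wilcoxon signed rank test. On the population it says "All subjects treated who have at least one follow-up will be included in the efficacy analyses". It gives no rule for a missing 3-month score, for scores obtained after a new medication, or for how a withdrawn subject counts in the responder rate. No sensitivity analysis is planned.

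The Synopsis (Additional Evaluations) states that every treated subject is followed to 1 year for informational purposes. The revision history, version C, gives as its reason for removing the analysis-population terms that all treated subjects will be analysed.

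**The concern.** The trigger is an event after treatment that is plausibly linked to the outcome. A subject with chronic rhinitis who gets little relief has an obvious reason to start a sino-nasal medication. Whether that subject then stays in the study can turn on the opinion of an investigator who knows the treatment given, because there is one arm and no described blinding. If such subjects are withdrawn before the 3-month visit, the paired analysis rests more heavily on those who did well.

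This matters more here than in a controlled trial. There is no comparison arm and no performance threshold, so the size of the improvement and the responder rate are the main efficacy results a reader will take away. Those are the quantities that selective loss can distort.

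**Working it through.** **Who drops out of the primary comparison.** Table 1 schedules the VAS NSS at screening, 1, 3, 6, 9 months and 1 year, and not at the 24-48 hour contact. Section 6.5 provides no visits after withdrawal, so I assume that no later scores are collected.

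- A subject withdrawn between 1 and 3 months has had a follow-up and belongs to the stated efficacy set, but supplies no baseline-to-3-month pair.
- A subject withdrawn after only the 24-48 hour contact may also count as having a follow-up, with no post-baseline VAS NSS at all.

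**The plan's own numbers.** Section 11.2 takes 30 subjects and allows for up to 20% loss: 30 × 1.20 = 36, as stated. Twenty percent of 36 is 7.2, so I use 7 as the upper case. The basis for 30 cannot be checked, since no effect size, SD or power is given.

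**Overstatement of the mean.** Let k of 36 be withdrawn before 3 months, and let f be their mean improvement (without the new medication) as a fraction of the completers' improvement. Both are assumptions. The all-treated mean is the completers' mean × [(36 − k) + k·f]/36, so the relative overstatement is 36/[(36 − k) + k·f] − 1.

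| k | f = 0 | f = 0.5 | f = 1 | f = 1.25 |
|---|---|---|---|---|
| 3 | 36/33 − 1 = 9.1% | 36/34.5 − 1 = 4.3% | 0% | −2.0% |
| 6 | 36/30 − 1 = 20.0% | 36/33 − 1 = 9.1% | 0% | −4.0% |
| 7 | 36/29 − 1 = 24.1% | 36/32.5 − 1 = 10.8% | 0% | −4.6% |

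**Responder rate.** Assume that 80% of completers respond, and count withdrawn subjects as non-responders. The rate is 0.80 × (36 − k)/36: 73.3% for k = 3, 66.7% for k = 6 and 64.4% for k = 7.

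**Significance test.** Assume a completer mean change of 2, SD 2.5 and k = 6. Among the 30 completers, t = 2/(2.5/√30) = 4.38, p = 0.00014. With six zeros added, the mean is 2 × 30/36 = 1.67 and the SD 2.40, so t = 1.67/(2.40/√36) = 4.17, p = 0.00019. With a weaker assumed effect (mean 1, SD 2.5, k = 7), p moves from 0.0400 to 0.0405. The added zeros lower the mean but also the standard error, so the test hardly changes.

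**Internal consistency.** The Synopsis commitment to follow all treated subjects to 1 year and the Section 6.5 permission to withdraw them cannot both hold for the same subject. The revision history shows the same intent as the Synopsis; I use it only as evidence of intent. Sections 6.3 and 6.5 also need reconciling: a study doctor may instruct a change of allergy medication, after which the same subject may be withdrawn for it.

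**The case against.** The strongest defence is that the rule protects the estimate: a score obtained on a new drug may credit the device with the drug's effect. That aim is sound, but withdrawal is a poor tool for it. Keeping the score and fixing its use in the analysis meets the same aim without losing the subject.

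The frequency may also be low. Withdrawal is permissive, subjects are asked not to change allergy medication, and exclusion E-L keeps out recent, unstabilised regimens. This limits the size but does not close the gap.

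Several stronger readings are tempting, and the documents do not support them:

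- *That the bias always favours the device.* The reason covers any medication or treatment, including one for an unrelated illness. If withdrawn subjects improved as much as completers there is no bias; if they improved more, the effect is understated.
- *That these subjects leave the data set.* Visits before withdrawal stay, and Section 11 keeps anyone treated with at least one follow-up. What is missing is a rule for the absent score.
- *That safety follow-up ends.* Section 8.1 follows adverse events until resolved, stabilised or explained, all treated subjects are in the safety analyses, and the safety endpoint is at 1 month. At most, scheduled detection of new events is lost.
- *That "Not eligible for treatment", also on the list, allows removal after treatment.* Sections 4.6.3 and 5 place the eligibility check and the handling of ineligible subjects before treatment. The natural reading is a screen failure.
- *That nothing can be repaired later.* An analysis that assigns no improvement needs only the baseline score and the documented medication start. The as-observed analysis does need the later scores.

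**Conclusion.** The concern holds as a risk, not as a demonstrated bias. A discretionary rule, with a trigger plausibly tied to poor relief, can selectively remove 3-month and later scores, and Section 11 does not say what happens then. The mean improvement and responder rate may be overstated; the conclusion of the paired test is unlikely to change.

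The 4% to 24% range rests wholly on assumed numbers withdrawn and assumed improvement. Its upper end assigns essentially the whole 20% loss allowance to this one reason, although Section 6.5 lists loss to follow-up separately, so it is a worst case. The primary endpoint is at 3 months. The 1-year data are informational, though they leave more time for such withdrawals.

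**What to change.** In Section 6.5, delete this reason for treated subjects. State that a treated subject who starts a medication stays in the scheduled VAS NSS, rTNSS and adverse event visits to 1 year, with the start date recorded on the concomitant-medication form. Add a phrase that ineligibility as a reason applies before treatment only.

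In Section 11, keep these subjects in the efficacy analysis and report the 3-month change in two ways: as observed, and with scores after a new sino-nasal medication set to no improvement (non-responder in the responder rate). Name in advance which is primary. That choice is open to debate: as-observed scores may credit the device with a drug effect, while assigning no improvement may understate benefit, for example after a short course for a cold. Reporting both shows how much it matters.

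The cost is a short amendment to two sections. The visits are already scheduled and concomitant medication is already collected. The estimate may be less favourable. The care a subject may receive does not change.

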7 INVESTIGATIONAL DEVICE ACCOUNTABILITY

Neurent Medical anticipates using one device per subject with an estimate of 36 devices total.

Device inventory will be managed using a Device Accountability Log that will include details concerning device receipt and disposition.

Access to device inventory will be controlled and both will be housed in a secure location. Records will be maintained to document the physical location of inventory from shipment/removal from Sponsor facility through use and/or return or disposal.

The site will be responsible for keeping records of receipt, use, and return or disposal of the investigation device, which shall include at a minimum, date of receipt, device identification number, expiration date, date of use, Subject identification code and date of disposition. The Device Accountability Log is provided for this purpose.

If the device is associated with a possible device-related adverse event or device deficiency, it should be prepared for disposition using proper protective procedures and returned to Neurent Medical for evaluation.

In the event of product return, Neurent Medical must be contacted for handling instructions prior to product return.

8 SAFETY MONITORING AND ADVERSE-EVENT REPORTING

8.1 Adverse Events

Adverse events (AEs) may occur during the investigational procedure or during the follow-up phase (see **Section 10** for potential risks). Adverse events occurring prior to the use of the NEUROMARK™ System will be documented in the patient's medical record but will not count as related to the investigational device or procedure.

An Adverse Event may occur in users or other persons. Such Adverse Events will be recorded and reported to the Sponsor.

- ☞ Should a user of the device, such as the physician, sustain an injury from the use of the device, the injury would be considered an AE.

Each AE will be judged by the Investigator as to its relationship and level of relatedness to the investigational device and/or investigational procedure. In addition, the Investigator will identify the date of onset, any required treatment or intervention, severity, and duration. All adverse events will be monitored until they are adequately resolved, stabilized and/or explained. Refer to **Table 3** and **Table 4** for Severity and Relationship categories and respective definitions.

The Investigator will use the following (**Table 4**) definitions to rate the severity of each adverse event:

Table 3: Adverse Event (AE) Severity

Severity	Description
Mild	→ awareness of a sign or symptom that does not interfere with the Subject's usual activity or is transient, resolved without treatment and → no sequelae
Moderate	→ interferes with the Subject's usual activity and/or → requires symptomatic treatment
*Severe	→ symptom(s) causing severe discomfort and → significant impact of the Subject's usual activity and → requires treatment

*If event is considered to be a Serious Adverse Event (SAE), the Investigator must report to the Sponsor the SAE within 24 hours of knowledge of the event.

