Unlikely	
 → little or no temporal relationship to the study procedure and/or → a more likely alternative etiology exists
Possible	
 → temporal sequence between procedure and event → is such that the relationship is not unlikely or → Subject's condition or concomitant therapy could have caused the AE
Probable	
 → temporal sequence is relevant or → event abates upon procedure completion or → event cannot be reasonably explained by the Subject's condition
Highly Probable	
 → temporal sequence is relevant and → event abates upon procedure completion/removal or reappearance of the event on repeat device application

Relationship	Description
Related	→ temporal sequence is relevant and → An adverse event that is not directly related to the use of the NEUROMARK™ System but is directly attributable to the procedure in which Neuromark was used.

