10.2 Potential Risks

Refer to the manufacturer's labeling for details concerning potential AEs associated with the use of materials, tools or fluid used during the procedure or immediately post-procedure.

Potential risks to the study Subject that may be associated with the use of the NEUROMARK™ System are as follows. Risk of these events is low.

- Allergic or other reaction to device materials or anesthetic (subjects are to be excluded if an allergy/potential allergy is known)
- Trauma to the nasal cavity including

- Mucosal bleeding
 - Mucosal damage
 - Pain/discomfort
 - Synechiae/Adhesions
 - Perforation
- Infection
- Impaired Nasal Function including:
 - Olfactory change
 - Worsening nasal obstruction
 - Septal perforation
 - Worsened eustachian tube function
 - Cosmetic deformity
- Atrophic rhinitis or dry nose
- Headache
- Bone necrosis
- Burn

There may be additional risks related to the local anesthetic including dermal allergic reactions, itching, rash, erythema, stinging and inflammation. Many of these side effects will subside quickly. Systemic side effects are rare and unexpected. They include arrhythmia, hypotension, and a system allergic reaction.

There may be risks related to any post-procedure medication prescribed by the Study Investigator. Those risks can be found on the medication's labeling from the manufacturer.

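### Section 8.1 prevents an anesthetic reaction that starts before device introduction from being rated procedure-related, and consented but untreated subjects have no scheduled adverse-event assessment, study ID or place in the safety analyses

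*Combined protocol and SAP*

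**What the plan says.** - **Section 8.1.** An event before the device is used is entered in the "medical record but will not count as related to the investigational device or procedure". No exception is given.
- **Section 6.1.** The local anesthetic comes first, immediately ahead of the device. Then: "Once the Subject is appropriately anesthetized, the NEUROMARK™ procedure may start".
- **Section 10.2.** Anesthetic reactions are among the listed risks. Of the systemic effects, which it calls rare, the section says: "They include arrhythmia, hypotension, and a system allergic reaction".
- **Section 8.2.** Table 4 has a procedure-related category that does not require the device to be the cause. The top grade of Table 6 covers an event that is not directly due to the device "but is directly attributable to the procedure in which Neuromark was used".
- **Table 1 and Section 6.2.** The first adverse-event mark in Table 1 is in the Immediately Post-Treatment column. Section 6.2 puts this check before discharge: "Assessment for any adverse events or issues".
- **Sections 5 and 5.1.** "Subjects will be considered enrolled once they are consented, meet eligibility criteria, and have received treatment". For someone who consents and then becomes ineligible, "the reason for ineligibility will be documented on the Screening Log". On identifiers: "At the time of enrollment, a unique study ID will be assigned to the Subject".
- **Section 11.** The safety analyses name treated subjects only.

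**The concern.** It is logical that an event before the device is used cannot be device-related. Extending the bar to the procedure does not follow, because the anesthetic is given for the procedure and carries risks that the protocol itself lists. Followed as written, Section 8.1 puts an early anesthetic reaction among the unrelated events, so a table of procedure-related events would omit a harm of the office procedure as patients receive it.

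The second strand concerns subjects who consent but are never treated, including one whose session is stopped because of a reaction to the anesthetic. The plan does not say how such a subject's event is looked for, identified in the database or presented in the report. Safety is half of the study objective, so both gaps matter, although neither reaches a primary endpoint.

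**Working it through.** No figure in the plan needs reproducing here. The check sets the sections side by side along the order of events on the treatment day.

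**Step 1. What may be rated as related, by time of onset** (taking device introduction as the start of use)

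| Onset of event | Device-related possible? | Procedure-related under Tables 4 and 6? | Procedure-related under 8.1? |
|---|---|---|---|
| After consent, before the anesthetic | No | Treatment session not begun | No |
| After the anesthetic, before device introduction | No | Yes | **No** |
| From device introduction onward | Yes | Yes | Yes |

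The conflict is in the middle row. An anesthetic reaction that starts after device introduction is unaffected.

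**Step 2. Does it depend on whether anesthesia is part of the procedure?** If it is, as its place under the 6.1 heading suggests, then 8.1 contradicts Table 4. If it is not, as the 6.1 sentence on when the procedure may start suggests, then a risk listed in 10.2 has no fitting category: Table 4 offers only procedure, device and pre-existing condition. Either way the text needs correcting.

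**Step 3. What survives for a treated subject.** The synopsis (Additional Evaluations) reports every adverse event whatever its severity or cause, and the check before discharge in 6.2 covers any event. The reaction can therefore be captured. What it loses is the procedure-related label. The anesthesia tolerability evaluations in 6.2 and 6.4 do not replace that label, since they are not relationship ratings.

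**Step 4. What survives for a consented, untreated subject**

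| Item | Provision |
|---|---|
| Serious-event report within 24 hours | Applies (Table 3 footnote, 8.3, 13.4); not limited to treated subjects |
| Scheduled adverse-event evaluation | None; the row starts Immediately Post-Treatment |
| Study ID | None; assigned at enrollment, which requires treatment (5, 5.1) |
| Identifier for CRFs and reports | The study ID (12.7, 13.4), which this subject lacks |
| Final accounting | 6.5 covers enrolled, hence treated, subjects |
| Safety analyses | Treated subjects named (11) |

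The Related grade of Table 6 is also worded for a procedure in which the device was used, so it does not literally fit a session stopped after the anesthetic.

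**Step 5. Effect on the endpoints.** The primary safety endpoint counts serious events attributed to the device at 1 month. A reaction before device introduction would not qualify under the present or the corrected rule. The efficacy analyses take treated subjects with at least one follow-up. Neither changes.

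**Step 6. Scale.** All 36 planned subjects receive the anesthetic before the device, but the documents give no reaction rate and no number of consented subjects, so no event probability can be stated. As an illustration only, suppose one treated subject has a reaction in the interval and no other procedure-related event occurs:

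- As written: 0/36 = 0%, exact 95% upper limit 1 − 0.025^(1/36) = 9.7%.
- Corrected: 1/36 = 2.8%, exact 95% interval 0.07% to 14.5%.

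**The case against.** The strongest reply on the anesthetic is that use of the System is not defined. Section 3.3 connects the device to the console before it mentions the anesthetic. If use begins at connection, the reaction comes after use has begun and can be rated. That reading is possible, but 6.1 points more naturally to introduction as the start, and the classification of a listed risk should not turn on the choice.

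Several stronger readings are tempting, and the documents do not support them:

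- **A reader might infer that early anesthetic reactions disappear from the safety data.** Section 8.1 removes relatedness. It does not keep the event off the CRF or out of the report of all adverse events.
- **A reader might infer that a serious event in an untreated subject will not reach the sponsor.** The 24-hour rule appears three times, once within 8.1 itself, and never with a treated-subject limit. The missing ID is not a bar either: 8.1 expects reports on users and other persons, who never have one, and the note in 13.4 gives confidentiality as its purpose. Consented subjects are on the screening log in any case (4.5).
- **A reader might infer from Table 1 that two whole columns before device use lack an adverse-event check.** The second column also holds the NEUROMARK treatment mark, so only Screening lies clearly before the device.
- **A reader might tie this to criterion E-J, on stopping anticoagulants or aspirin.** E-J is an exclusion and does not order a drug to be stopped; E-P and E-S let the investigator keep out anyone at risk. Who approves a stop is an eligibility matter, separate from this point.

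What stands is the conflict between 8.1 and Tables 4 and 6, and the smaller gap in scheduling, identification and analysis for untreated subjects.

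**Conclusion.** The point holds and is minor. Section 8.1 misclassifies an anesthetic reaction that starts between administration of the anesthetic and introduction of the device. For treated subjects the loss is confined to the procedure-related classification. For consented, untreated subjects the serious-event reporting duty remains, but scheduled assessment, a study identifier and a place in the analysis are missing.

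The affected interval is short and 10.2 describes systemic anesthetic effects as rare, so few events, if any, are likely to be involved.

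The conclusion assumes that use of the System begins at device introduction. It also assumes that nothing in the Instructions for Use, Investigator's Brochure, consent form or Appendix F, none of which was available, sets a different rule. The definitions in Section 16 say that the Instructions for Use cover delivery of the local anesthetic, so that document should be checked first.

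**What to change.** 1. **Section 8.1.** Replace the sentence on events before device use with, for example: *Events before device use are not rated as device-related. Events from administration of the local anesthetic onward are recorded on the AE CRF and rated against the study procedure (Table 6). SAEs from informed consent onward are reported to the Sponsor within 24 hours, whether or not the subject is treated.* Extend the Related description in Table 6 to a session stopped before the device is used.
2. **Section 5.1.** Identify untreated subjects by a screening number, accepted on CRFs and reports in place of the study ID.
3. **Section 11.** List SAEs and anesthetic reactions in consented, untreated subjects separately, beside the primary safety endpoint, which stays as defined.

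The cost is wording only, with no added visit. The downside is a few extra adverse-event records and possibly a slightly higher count of procedure-related events.
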